## STUDY DESIGN OVERVIEW

### STUDY HYPOTHESIS AND RATIONALE

The study hypothesizes that effective communication could be part of prevention and treatment for ICU-delirium in critically ill, mechanically ventilated patients.

Lack of communication is a common, unmet need for these patients. It is believed that effective communication deprivation could be a contributing factor to the development of ICU delirium. It is further hypothesized that this communication gap could be matched by a wearable, eye-tracking-based communication device.

EyeControl is a wearable, easy-to-use device that could supplement current communication methods between the patient and the treating team (and family). Current standard of communication for the critically ill mechanically ventilated patients is limited to nodding, writing, and pointing at communication boards. The wearable device could potentially allow broader and more effective communication. It may have secondary benefits as well, as a monitoring device, an emergency-call device, and to improve patients' orientation.

### STUDY DESIGN AND METHODS

This is a two-step trial, that will first have a “burn-in” phase to gain real-life experience with the device in critical care settings, and later in the second step transition into a randomized controlled study that measure the efficacy of the communication intervention on prevention and treatment of ICU-delirium. The study will be run across all ICUs at Emory University Hospital, a large, tertiary referral center. The different ICUs are detailed in Table 1.

#### STEP 1: ASSESS THE SAFETY, TOLERABILITY, AND EASE OF USE OF THE EYECONTROL DEVICE

On a daily basis all patients admitted to any of the ICUs at EUH will be screened for participating in the trial. Since during admission the patient could be first excluded and later meet inclusion criteria, the screening will continue for all patients on a daily basis (for inclusion/exclusion criteria, see below).

During screening, the patients' EMR will be accessed and/or their clinical status will be discussed with the treating team (RN, APP, MD) by a member of the study team in order to identify whether they meet inclusion/exclusion criteria. For example, the study-team personnel will identify if the patient is ventilated, for how long, and what is the patient's wakefulness and cooperation by nursing charting (e.g., RASS scale, nursing neurological and clinical assessment).

Of note, due to the different nature of neurologically injured patients in these settings (primary organ effected is the brain), we will enroll about 33-50% of the patients in this step from the neuroscience ICU. This approach will allow us to consider re-defining our parameters in the second step of the trial and design a pre-defined subgroup analysis.

Upon meeting inclusion criteria, patients and/or their LARs will be approached for consent (see below for consent process details). Consented patients will be instructed how to use and operate the EyeControl device. The primary outcome of this part of the study will be time to operate the device. Successful operation will be defined as the ability to use the device to call for help, and produce one predefined sentence out of several options, three different times.

Once the patient is able to operate the device, it will stay on the patient for as long as she or he would like it on, or until the patient is successfully extubated or discharged from the ICU, whichever is earliest. During the time the patient is wearing the device, apart from its original intention to serve as a communication device, the following features will be activated and tested:

- a. Emergency call—if the patient is in distress, she or he could call for help by simply blinking three times. This will initiate a call for help from the device. We will monitor the use of this emergency call, its frequency, and causes for calling.
- b. Wakefulness monitoring—the device will record the times in which the patient is awake by monitoring when the patient's eyes are open. This data will later be correlated with outcome measures such as delirium, LOS, and functional outcome. Changes in wakefulness time will also be correlated with ICU interventions such as adding a melatonin-agonist to promote sleep.
- c. CAM-ICU validation—every shift, after the nurse and/or study team member assesses CAM-ICU, the device will repeat the test by using multiple-choice questions and ask the patient to choose the correct answers by blinking. We will later correlate the device's results with the nursing/study team ones.
- d. Reorientation – at a defined time interval, if the patient's eyes will be open, the device will read the patient the current date/time/location.
- e. Entertainment – patients will have the option to listen to music.
- f. Family communication – Families will be supplied with a patient-unique link to record audio messages which the patient will be able to listen to through the device.

To address the secondary goal of proficiency with device operation, we will administer a daily orientation questionnaire via the device. If a patient fails this proficiency check, study staff will perform a device re-training module. The frequency and amount of necessary re-training will be captured as another data parameter.

During the study, we will collect clinical information from the patient's chart including: demographics, diagnoses, use of sedatives or medications that could change cognitive function, nursing charting (including neurological assessment), laboratory results, days on the ventilator, procedures, discharge destination, mortality, and functional outcome. All of these will be taken into account for the final analysis of the study. For example, this data could help us better identify which patients used the device more than others and which could benefit from its monitoring properties apart from its communication function.

As part of its operation, the device captures photographs and video of the patient's eyes (figure 3). In addressing the secondary goal of potential correlation between eye behavior and clinical events, we will explore this possibility by evaluating photographs of the eyes at the times of clinical events (i.e. hypoxia, new onset shock, or new onset sepsis). The device will activate the image data collection only after 50 consecutive frames of eye-in-the-image. This should be a safety index to verify that the device is only recording the eye. It will stop recording immediately when non-eye-in-the-image occurs. Data processing to decide if an eye is in the image is done locally on the device, so eventually only images of eyes should be collected. All external image data processing will be done following deidentification of the data, using the patient code only as an identifier.

Figure 3. Example photographs captured by the EyeControl device.

No randomization or blinding is planned for this step of the study, and no samples are planned to be collected.

---

**STEP 2: MEASURE REDUCTION IN DELIRIUM-FREE AND ALIVE DAYS IN THE ICU WITH EYECONTROL-BASED COMMUNICATION COMPARED WITH THE STANDARD OF CARE.**

The second step will be similar to the operation of the first one, in terms of patient screening and enrolling. The main difference will be the randomization process. Patients will be randomized to use EyeControl for as much as they wish, versus the standard of care. Randomization will be done centrally, and will be stratified to the specific unit, gender and age, race and ethnicity.

The primary goal of the second step will be to measure the time spent alive and non-delirious in the ICU with EyeControl-based communication compared with the standard of care. Delirium will be defined as CAM-ICU positive, starting at day 1 of use (following the day of training), up to 14 days from randomization or ICU discharge, the earliest. However, patients could require moderate to deep sedation following randomization, for example due to new or evolving medical complication. Whenever the RASS is below (-1), CAM-ICU will not be measured, and will be charted as undetermined. Therefore, only days in which the patient will be CAM-ICU positive, will be counted towards the primary outcome. CAM-ICU positive days prior to randomization will not be counted towards the primary outcome.

[figure not shown]
The secondary outcomes will include the following:

1. Assess the safety, tolerability, and ease of use of the EyeControl device. This will be achieved by daily review of advance events, and ask patients, families and clinical team regarding challenges of use.
2. Measure the length and intensity of use; We will measure time to first activation, as detailed under the primary goal of the first step, and on a daily basis we will collect data from the device including the number of hours a day the device was worn, how many times it was used for communication, and the type of communication (eg use of predefined sentences, call for help, using new sentences by dictation, entertainment listening etc).
3. Correlate between the monitoring data and clinical data, specifically validate CAM-ICU with nursing and/or study team independent assessment; and correlating wakefulness time with ICU interventions; We will collect from the device on a daily basis the times when the patient has his or hers eyes open, as a marker of wakefulness. We will also record interventions related to sleep and wake cycles, such as administration of

Melatonin or Melatonin agonists, night time antipsychotics, benzodiazepines etc. We will also perform a correlation between the device independent assessment of CAM-ICU, and the clinical team assessment.

- Measure the cognitive and functional long-term outcomes, by phone questioners, to be done in a blinded fashion at 6 months from ICU discharge. This will include a pre-defined battery of tests, as detailed under the Long-Term Outcomes (LTO) Battery section below.

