#### Secondary goals:

1. Assess the safety, tolerability, and ease of use of the EyeControl device; Specifically, we will assess on a daily basis for any adverse events related to the device. We will also document need for re-training on the device as a marker for ease of use.
2. Measure the length and intensity of use for communication and call for help; Intensity will be measured by the number of times the device is used and for which purpose as a categorical measure (eg, call for help, talk using predefined sentences, communicate using letter by letter dictation etc).
3. Correlate between the monitoring data and clinical data: the device will assess CAM-ICU independently, and a study team member will repeat this analysis and the documented results will be documented. We will also track any clinical decision making based on wakefulness time information (for example a decision to add melatonin agonist to promote sleep) ;
4. Measure the cognitive and functional long-term outcomes, by phone questioners, to be done in a blinded fashion at 6 months from ICU discharge.

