## STATISTICAL ANALYSIS PLAN

**Step 1:** Step 1 of the present trial focuses on describing device usage and acceptability. Continuous data will be described using medians and interquartile ranges. Categorical variables will be described using frequencies, percentages, and 95% confidence intervals. No statistical hypothesis testing will be conducted.

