### Step 2:

Primary Outcome: The time spent alive and non-delirious in the ICU

Covariates/Confounders: age, gender, race, baseline education level, unit to which the patient was admitted to, need for tracheostomy, severity of illness by SOFA or APACHE score on admission and randomization day, categorical reason for admission (e.g. sepsis, ARDS, elective surgery, stroke etc), diagnosis of delirium prior to randomization and the presence of an acute central neurological injury.

Unadjusted Analyses: The time spent alive and non-delirious in the ICU will be evaluated using the stratified variant of the Mann-Whitney U test. In this analysis, patients will be stratified by ICU setting. For other variables, the unadjusted comparison will depend on the type of variable. In general, continuous variables will be compared using a Mann-Whitney U test and categorical variables will be compared using the  $\chi^2$  test.

Adjusted Analyses: The time spent alive and non-delirious in the ICU will be evaluated using a multi-level/mixed-effects quantile regression (median/50th percentile) while controlling for the previously listed covariates. The multi-level/mixed-effects model will be used to account for clustering within ICU setting. In the event that the regression fails to estimate properly, the covariates will be used to generate propensity scores and patients will be stratified into  $\geq 5$  propensity score strata. The time spent alive and non-delirious in the ICU will then be analyzed using the stratified variant of the Mann-Whitney U test. Analyses of the secondary outcomes will depend on the type of variable. Continuous variables will be analyzed using multi-level/mixed-effects quantile regressions (median/50th percentile), binary variable will be analyzed using multi-level/mixed-effects binary logistic regressions, ordinal scales will be analyzed using multi-level/mixed-effects ordinal (cumulative logit) logistic regressions.

Missing Data: In the event of substantial missing data, data will be imputed using a multiple imputation procedure. The type of procedure (e.g. fully conditional specification, hot decks etc.) and the number of imputed data sets will be determined by the amount of missing data and the pattern of missingness.

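### Wakefulness is to be correlated with sleep interventions that the wakefulness reading may itself prompt, and the analysis has no term for the reading before the intervention

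*Combined protocol and SAP*

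**What the plan says.** All places are in the combined protocol and SAP.

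- **Study Design and Methods, Step 1, item b (wakefulness monitoring):** "Changes in wakefulness time will also be correlated with ICU interventions such as adding a melatonin-agonist to promote sleep". No comparator, time window or model is named. The same section lists chart data to be collected, including sedative use and ventilator days, and adds: "All of these will be taken into account for the final analysis of the study".
- **Study Purpose, Step 2, secondary goal 3:** "We will also track any clinical decision making based on wakefulness time information (for example a decision to add melatonin agonist to promote sleep"). The example is the same intervention that Step 1 names.
- **Study Design and Methods, Step 2, secondary outcome 3:** the aim is repeated as "correlating wakefulness time with ICU interventions". This concerns the level of wakefulness, not its change. The data are daily: "We will collect from the device on a daily basis the times when the patient has his or hers eyes open, as a marker of" (the sentence then names wakefulness). Sleep-related drugs are recorded as well, among them melatonin agonists, antipsychotics given at night and benzodiazepines.
- **Statistical Analysis Plan, Step 1:** descriptive only. "No statistical hypothesis testing will be conducted".
- **Statistical Analysis Plan, Step 2:** the covariate list begins "Covariates/Confounders: age, gender, race, baseline education level, unit to which the patient was admitted to, need for tracheostomy" and goes on to illness severity, reason for admission, delirium before randomization and acute central neurological injury. It contains neither a prior wakefulness value nor ICU day. Continuous secondary outcomes get mixed-effects median regression, with clustering by ICU setting. No term for repeated days within a patient is named.

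**The concern.** A sleep-promoting drug is more likely to be added after a day with much recorded wakefulness, if staff act on that record. The high reading is then both the reason for the intervention and the first half of the change score. A high reading tends to be followed by one nearer the average whatever is done, so patients who start the drug show a larger fall than those who do not.

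The Step 2 version, which uses the level, errs in the opposite direction. Patients who start the drug were more wakeful to begin with and remain somewhat more wakeful the next day, so the drug appears to go with more wakefulness.

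At stake is the secondary aim of relating the device's monitoring data to clinical data. As planned, an association could reflect a signal that responds to care, or only selection on that signal, and the analysis cannot tell them apart. This would be so even with complete 24-hour recording.

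**Working it through.** The plan gives no figure for this analysis, so there is none to reproduce.

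**Inputs.** From the plan: daily readings, an intervention that may be prompted by the reading, and no prior-value term. Assumed, because the plan is silent: the day-to-day correlation ρ of wakefulness, and how strongly the reading drives the start. Results are in SD units, and the true effect of the intervention is set to zero.

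**Step 1: formulas.** Let D be the gap in the pre-intervention reading between those who start and those who do not. Under bivariate normality with equal variances and no effect:

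- expected difference in change = -(1 - ρ) × D
- expected difference in next-day level = +ρ × D

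Both are zero only if D = 0, that is, if starting is unrelated to the reading (leaving aside the limiting values ρ = 1 and ρ = 0).

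**Step 2: graded trigger.** The probability of starting is logistic in the reading, with intercept -1.1 and log-odds slope 0.5 or 1.0 per SD (odds ratio 1.65 or 2.7).

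| Odds ratio per SD | Share starting | D | Change, ρ = 0.5 | Next-day level, ρ = 0.5 |
|---|---|---|---|---|
| 1.65 | 26% | 0.353 + 0.124 = 0.477 | -0.5 × 0.477 = -0.24 | +0.24 |
| 2.7 | 29% | 0.604 + 0.242 = 0.845* | -0.5 × 0.845 = -0.42 | +0.42 |

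*From unrounded means.

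For other values of ρ, the difference in change is:

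- ρ = 0.3: -0.7 × 0.477 = -0.33 and -0.7 × 0.845 = -0.59
- ρ = 0.7: -0.3 × 0.477 = -0.14 and -0.3 × 0.845 = -0.25

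**Step 3: fixed threshold.** If the highest 25% of readings all prompt the intervention, their mean is 1.27 SD above average. The expected fall among those treated is (1 - ρ) × 1.27, which is 0.89, 0.64, 0.38 or 0.13 SD for ρ = 0.3, 0.5, 0.7 or 0.9. Over thresholds from the top 10% to the top 50%, and ρ from 0.3 to 0.9, the fall ranges from 0.08 to 1.23 SD.

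**Step 4: does the proposed term remove it?** In a simulation of 200,000 patient-days with no true effect and a steeper logistic trigger (slope 1.5 per SD), the treated-minus-untreated differences were:

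| ρ | Crude change, no time trend | Crude change, recovery trend | Adjusted for prior value, or prior value and ICU day |
|---|---|---|---|
| 0.3 | -0.77 | -0.75 | within 0.02 of 0 |
| 0.5 | -0.56 | -0.53 | within 0.02 of 0 |
| 0.7 | -0.33 | -0.33 | within 0.02 of 0 |

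When starting did not depend on the reading, the crude difference was also about zero. Adding ICU day to the prior value changed the estimate very little.

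**The case against.** The strongest reply is that the plan claims less than a critic may read into it. Five points have weight.

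- **Cause of starting.** A reader might infer that the interventions are started because of the reading. The documents do not say so. They say that decisions based on it will be tracked, in Step 2 only. Sleep drugs can be started for other reasons, and where they are, this bias is absent.
- **Causal credit.** A reader might infer that the plan credits the fall to the intervention. It speaks only of correlation, so that would be a misreading of the result, not a stated aim.
- **False positives.** A change score tested at 5% under the two graded triggers, at ρ = 0.5, would be significant in about 22% and 57% of trials with 124 patients, against about 5% after adjustment. The documents do not plan that test: Step 1 rules out hypothesis tests, and the Step 2 text has no change score. These rates only illustrate the mechanism.
- **Recovery over time.** A reader might add recovery and sedation weaning as a second source of bias. In the simulation a recovery trend barely moved the result. The case rests on the prior value.
- **Existing adjustment.** The plan does promise to take chart data into account and does specify mixed models. Neither includes the prior wakefulness reading, so neither removes the bias.

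What remains is a narrower point. The analysis as worded is biased, descriptively or otherwise, wherever the reading prompts the intervention, and the protocol itself foresees that this can happen.

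**Conclusion.** The point holds as a minor one about an exploratory secondary analysis. Where the wakefulness reading prompts a sleep intervention, the Step 1 change correlation is biased downward and the Step 2 level correlation upward under no effect. At ρ = 0.5 and odds ratios of 1.65 to 2.7 per SD, the spurious difference in change is about -0.24 to -0.42 SD. It would be smaller with steadier readings or a weaker trigger, and zero if starting does not depend on the reading.

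The directions assume that higher wakefulness makes a start more likely. The plan gives neither the correlation nor the strength of the trigger, so the figures are illustrations and not predictions for this trial. The Step 2 primary comparison between arms and its sample size of 248 do not depend on this analysis.

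**What to change.** In Step 1 item b and Step 2 secondary outcome 3, and correspondingly in the Statistical Analysis Plan, replace the simple correlation with wording such as:

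> Next-day wakefulness time will be modelled on whether a sleep intervention was newly started, using patient-days with and without a new start. The model will adjust for wakefulness on the day before the intervention and for ICU day, and will allow for repeated days per patient by a random effect or patient-clustered standard errors. In Step 1 the estimate will be reported descriptively. In both steps it will be reported as an association only.

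The day-before value is the essential term; ICU day is a sensible addition. The adjustment works to the extent that starting depends on the recorded reading. Other reasons for starting can still confound the result, hence the restriction to association.

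The cost is a change of wording and a slightly more complex exploratory model. The daily wakefulness times and the sleep-related interventions are already to be collected.

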#### Secondary Goals:

1. Assess the proportion of mechanically ventilated, critically ill patients, with or without primary neurological injury, who could benefit and operate an eye-movement-tracking device as a means of communication.
2. Assess the type and length of the use done by the patient. For example, we will monitor how long a patient wears the device, uses it, and for what purpose (communication, call for help or entertainment).
3. Assess the EyeControl device as a diagnostic/monitoring tool for delirium in comparison to the bedside nurse assessment. Specifically, the device will record times of wakefulness for each 24h period of time, and will test for delirium using CAM-ICU. The later will be correlated with a live, verbal assessment done by a study team member.
4. Assess patient proficiency in device operation through daily orientation questionnaire.
5. Assess the change in level of frustration and discomfort patients and families feel in relation to communication with and without the device. These will be assessed by a questionnaire given to patients and families near their discharge.
6. Explore possible correlation between eye movements and clinical events by evaluating photographs of the eyes at the times of these events.

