### EXCLUSION CRITERIA

- < 18 years of age
- Not admitted to the ICU
- Inability to follow commands during screening (at a minimum: open and close eyes, move eyes to one side or the other).
- Known cerebral injury (acute or chronic) in the dominant hemisphere concerning for aphasia on clinical assessment
- Significant pre-existing neurologic (i.e., dementia and/or cognitive deficiencies), hearing loss (with inability to hear through a bone-conduction speaker), psychiatric, or baseline communication challenges that would confound outcomes assessments
- Inability to blink or move eyes for any reason
- Prisoner or incarceration
- Inability or unwillingness to provide informed consent
- Unwillingness to be contacted for follow-up

Patients who meet the inclusion and do not meet any exclusion criteria will be approached for consent, as will be described below.

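### The device CAM-ICU is compared with the clinical one only when patients can and choose to use the device, with no rule for uncompleted tests; a completed-pairs analysis is likely to overstate detection of delirium

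*Combined protocol and SAP*

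**What the plan says.** The aim is diagnostic. Study Purpose, Step 1, secondary goal 3 reads: "Assess the EyeControl device as a diagnostic/monitoring tool for delirium in comparison to the bedside nurse assessment". The Step 2 secondary outcomes (item 3) repeat it: "specifically validate CAM-ICU with nursing and/or study team independent assessment".

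Access to the test in Step 1 is conditional (Study Design and Methods, Step 1). "Once the patient is able to operate the device, it will stay on the patient for as long as she or he would like", or until extubation or ICU discharge. During wear, "the following features will be activated and tested", and the CAM-ICU is item c of that list. It follows the clinical CAM-ICU each shift, and the patient answers by blinking: "the device will repeat the test by using multiple-choice questions and ask the patient to choose the correct answers by blinking".

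The analysis is given in one sentence: "We will later correlate the device's results with the nursing/study team ones". The Step 2 text also promises a correlation. The Statistical Analysis Plan makes Step 1 descriptive. For Step 2 it sets out comparisons and regressions. It names no measure of diagnostic accuracy or agreement for the device CAM-ICU and no denominator.

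Two provisions deal with CAM-ICU values or data that are not obtained. In Step 2, a CAM-ICU at RASS below -1 is charted as undetermined, in the context of the primary outcome. Under the Step 2 heading of the SAP, multiple imputation is to be used if missing data are substantial, with the method chosen later.

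**The concern.** A delirium monitor is useful to the extent that it works in delirious patients. Delirium plausibly makes it harder to learn the device, tolerate it and finish a test answered by blinking. The protocol itself lists delirium among the causes of communication difficulty and describes it as fluctuating. A patient can therefore pass the command-following check at entry, become delirious later and then give no device result.

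Such a shift has a clinical CAM-ICU but no device CAM-ICU. A correlation of paired results has nothing to use there. If non-completion is more common on delirious shifts, the remaining pairs over-represent shifts on which the patient could cooperate. Their agreement could then be read as the performance of the device in ventilated patients generally.

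**Working it through.** The documents give no accuracy target, completion rate or sample size for this validation, so there is no stated figure to reproduce. The check has two parts: reading the provisions together, and an illustration on assumed inputs.

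**Does another provision fill the gap?**
- The RASS rule covers sedation below -1. It does not cover a patient at RASS -1 or above who cannot or will not complete the device test.
- The imputation clause stands under Step 2 and is general. The Step 1 analysis text has no missing-data rule. Imputation is also a poor fit: a test the patient could not finish is a failure of the tool, not an unknown value to be filled in.
- The daily proficiency check with re-training may reduce non-completion. It does not say how non-completion is recorded or scored.

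**Illustration 1: sensitivity with non-completions counted as missed**

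Assumed: sensitivity among completed tests s = 85%; completion on clinically delirious shifts c = 80% or 50%.

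Share of delirious shifts detected = s × c:
- c = 80%: 0.85 × 0.80 = 68%
- c = 50%: 0.85 × 0.50 = 42.5%, about 43%

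A completers-only analysis gives 85% in both cases.

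**Illustration 2: dependence on the scoring rule**

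Assumed: sensitivity and specificity 90% among completed tests; completion 60% if delirious and 95% if not. The protocol's Sample Size section cites a delirium rate of about 50%; it is borrowed here as a share of shifts and affects only overall accuracy.

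| Non-completions | Sensitivity | Specificity | Overall accuracy |
|---|---|---|---|
| Left out | 90% | 90% | 90% |
| Scored negative | 0.90 × 0.60 = 54% | 0.90 × 0.95 + 0.05 = 90.5% | (54 + 90.5)/2 = 72% |
| Scored as failure | 54% | 0.90 × 0.95 = 85.5% | (54 + 85.5)/2 = 70% |
| Scored positive | 0.54 + 0.40 = 94% | 85.5% | (94 + 85.5)/2 = 90% |

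With completion on delirious shifts varied from 50% to 95%, sensitivity over all shifts runs from 45% to 85.5% if non-completions are scored negative or as failures, and from 95% to 90.5% if scored positive. The completers-only figure stays at 90%.

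Leaving non-completions out therefore overstates sensitivity under the first two scoring rules. Under the third it slightly understates sensitivity and overstates specificity (90% against 85.5%).

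**The case against.** The strongest reply is that the plan is silent rather than wrong. A reader might infer that it discards unfinished device tests, but no sentence says so; losing those shifts is the default consequence of correlating pairs. A reader might also infer that it will publish an inflated sensitivity. It names a correlation, not sensitivity, so it cannot be said that it would report 85%. Both points stand.

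The direction is not fixed either. The patient is asked to choose correct answers, so a wrong answer is a completed result, not a missing one, and the scoring of a non-answer is unstated. As the second illustration shows, scoring non-completions as positive reverses the effect on sensitivity. This also stands, with one limit: a device that is not being worn cannot flag delirium, so scoring those shifts positive is hard to defend.

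Much of the context is already planned. The proportion of patients able to operate the device is an outcome, Step 2 compares successful with unsuccessful patients, daily hours of wear are collected in Step 2, and re-training is recorded. Readers would see failure to learn and, in Step 2, non-wear at patient or day level. They would not see completion and reason for each scheduled test, set against the clinical result.

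Finally, the requirement to operate the device first is written for Step 1. The Step 2 text says that patients use the device as much as they wish and does not restate the requirement. The documents therefore support voluntary use in Step 2, but not the same gate.

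**Conclusion.** The point holds as a gap with a likely direction. In Step 1 the comparison is confined to patients who have learned the device, while they choose to wear it. Step 2 repeats the validation under voluntary use. Neither step has a rule for device tests not attempted or not finished. If only completed pairs are analysed, the result is likely to overstate how well the device detects delirium, chiefly its sensitivity.

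This rests on two assumptions: that delirium lowers completion, which is plausible but not quantified in the documents, and that a non-completed test counts as a missed or failed detection. The size is unknown. The fall from 85% to 68% or 43% shows scale on assumed inputs and is not an estimate for this trial. The stronger claim that accuracy will be overstated is not supported.

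The matter concerns a secondary goal, described in the Synopsis as proof of concept for the burn-in phase. No effect on the Step 2 primary comparison is claimed. It is still worth correcting, because the aim is diagnostic in both steps and completion status not logged at the time may be unrecoverable.

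**What to change.** For each shift with an assessable clinical CAM-ICU:
- Record the device result as positive, negative or not completed, with the reason: not yet able to operate the device, not worn by choice, or unable to answer.
- Tabulate these three categories against the clinical result, and report completion by clinical CAM-ICU status.

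In the SAP, replace the bare correlation with sensitivity and specificity, reported both among completed tests and over all assessable shifts. Specify in advance how non-completions are scored for each measure. Use confidence intervals that allow for repeated tests in the same patient.

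Show chosen non-wear separately from inability to answer. A headset removed by preference is a matter of uptake, and merging it with failed tests would blur uptake with accuracy. For the same reason, both denominators should be shown rather than the all-shifts figure alone. Limit any completers-only conclusion to patients able and willing to use the device.

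The cost is one status field per shift and some SAP wording; the clinical CAM-ICU is already scheduled every 12 hours. The reported accuracy is likely to look less favourable.
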